2. PROTOCOL SYNOPSIS

Name of Sponsor:	[name].
Name of Investigational Product:	Spironolactone
Name of Active Ingredient:	Spironolactone
Study Title:	A randomized open label pilot trial of spironolactone versus prednisolone in corticosteroid-naïve boys with DMD
Study Number:	N=24
Sponsor-Principal Investigator:	[name].
Clinical Study Phase:	Pilot Study
Number of Centers:	Four to seven centers
Study Duration:	6 months. Subjects will undergo strength and functional testing at screening (Day -14 to 0) and monthly electrolyte testing. Follow up strength and functional testing will occur on Days 90 and 180. After 6 months of treatment, all subjects will be offered standard glucocorticoid therapy based on their local clinic's standard of care or continued dosing on the medication taken during the trial if there is clear established efficacy.
Study Design:	Randomized, open-label, pilot clinical trial of spironolactone suspension versus oral prednisolone
Study Objectives:	To determine if 6 months of treatment with either spironolactone or a standard clinical dose of corticosteroids results in equivalent improvement in time to complete the 100 meter timed test (100M). To assess the safety of spironolactone treatment in the steroid naïve DMD population.
Patient Population:	Inclusion Criteria: 
• Duchenne muscular dystrophy (DMD) patients ≥ 4 to ≤ 7 years of age• Clinical features of DMD that include proximal predominant weakness and/or gait disturbance• Presence of a truncating mutation of the DMD gene in the patient or an affected male relative OR a muscle biopsy that demonstrates $<5\%$ dystrophin in the patient or an affected male relative• Normal left ventricular ejection fraction by screening echocardiogram• Ability to cooperate for testing

	
• No prior treatment with glucocorticoids or vamorolone• No concomitant experimental therapies
	
Exclusion Criteria:
 
• Subject amenable to or currently being treated with eteplirsen, golodirsen, casimersen, or viltolarsen• Hyperkalemia at screening• History of or ongoing renal failure (elevated creatinine, oliguria, anuria)• Hypersensitivity to spironolactone (rash, respiratory distress, arrhythmia, numbness or tingling of extremities)• Current treatment with an ACEi• Severe peptic ulcer disease or recent gastrointestinal perforations

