Study Procedures:	Subjects will receive either prednisolone or spironolactone. Strength and functional testing will occur at screening (Day -14 to 0) and at 90 and 180 days after initiation.
Study Outcomes:	
Primary:
 
• Time to complete the 100 meter timed test (100M) 
Secondary:
 
• Muscle strength as measured by dynamometry score, a composite score made up of values from maximum voluntary isometric contraction testing of the flexors and extensors of the elbows and knees, as measured in kilograms of force.• North Star Ambulatory Assessment (NSAA), a functional scale validated in the DMD population• 4-stair climb• Time to arise from floor 
Exploratory:
 
• Safety measures• Biomarker studies
Sample Size:	A total of 24 subjects are expected to be enrolled in this trial, with 12 randomized to each treatment group. 
• Treatment Group 1: Spironolactone 1 mg/kg/day (n=12 subjects)• Treatment Group 2: Prednisolone 0.75 mg/kg/day (n=12 subjects) or weekend dosing per the sites standard of care

Statistical Analysis:	
Age-corrected 100M will be considered as the primary outcome, and will be evaluated using a two-one-sided t-test to test equivalency between treatment arms in the change from baseline to 6 months. In addition, repeated measures ANOVA will be used to determine whether the trajectory across all three time points (baseline, 3mo, 6mo) differs by treatment group. Strength testing/dynamometry, NSAA, 4-stair climb, and time to arise from floor scores will be secondary outcomes, and will also be compared by treatment group using repeated measures ANOVA. Biomarkers studies will be considered exploratory outcomes.
 
Power: Prior studies evaluating the 100m walk test among patients with DMD have shown an average change over 6 months of -2.9 ±7.8. An effective sample size of 10 patients per group will provide 80% power to declare equivalency with an equivalence margin of ±10.6.

Long-term follow-up:	All adverse events will be followed until resolution or stabilization.

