The pilot trial we propose will directly answer the question of whether spironolactone is as efficacious as prednisolone over 6 months of treatment in young patients (age ≥ 4 to ≤ 7 years) with DMD, as judged by the age-corrected 100 meter timed test and by dynamometry scores derived maximum voluntary isometric contraction testing of selected muscles and the time to climb 4 stairs. For steroid-naïve patients, this could delay institution of prednisolone therapy – considered the standard of care – for up to 6 months. However, it is important to recognize that not all DMD parents choose for their boys to go on steroids during this age window, and that there is no clear evidence based consensus of when treatment must be initiated. Finally, we note that published data from [name] lab and others demonstrates that prednisolone results in increased cardiac deterioration in the mdx mice, suggesting cardio-toxic effects on dystrophic heart^{11, 17}. Therefore, we feel that delaying onset of steroid therapy is justified for this pilot trial in order to gain meaningful pilot data regarding spironolactone in DMD patients, and note that all subjects will be offered open label prednisolone therapy as a standard of care after completion of the trial. If there is equal or greater efficacy with spironolactone, they may choose to continue on spironolactone.

In this pilot trial we will use prednisolone since it is delivered as an oral suspension. Since the standard of care regimen (daily versus weekend dosing of prednisolone) differs from site to site, each PI will have the discretion to assign subjects to their preferred regimen. Equal efficacy has been shown between daily and weekend dosing regimens¹⁸.

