5.2 Rationale

DMD is a devastating disorder of childhood, leading to loss of ambulation by age 12 years, and typically to death between 20 and 30 years. Until recently, the only treatment shown to improve strength and preserve ambulation in DMD patients was the use of glucocorticoids, which are accompanied by significant side effects. Recent developments in gene corrective therapies (such as the exon-skipping oligomer eteplirsen or the nonsense-suppression compound ataluren) represent potential therapies only for those relatively small subsets of patients with mutations that are amenable to that specific corrective mechanism (around 13% and 15% of DMD patients, respectively)¹⁹. We wish to determine whether another commonly used medication, spironolactone, may have similar beneficial effects with a lower side effect profile and be applicable to a wider population of DMD patients.

Our hypothesis for this controlled pilot trial is that spironolactone and prednisolone are of equal efficacy in improving skeletal muscle function over a 6-month period, and that spironolactone will be well tolerated in this patient population.

One outcome is that both drugs demonstrate equal efficacy in motor function. This would then serve as pilot data for a longer term study.

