6. OBJECTIVES AND PURPOSE

6.1 Primary Outcome

The primary objective of this trial is to determine whether spironolactone has similar efficacy to glucocorticoids in improving muscle strength in steroid naïve DMD patients. Glucocorticoids are the only medications that have been shown to change the clinical course of Duchenne muscular dystrophy, but have significant side effects (e.g., obesity, cushingoid features, osteoporosis, and behavioral disturbances). Preclinical data suggests a significant protective effect from spironolactone in the mdx and mdx;utrn^{+/−} animal models. We propose a randomized, open-label pilot trial comparing spironolactone to prednisolone.

The primary outcome measure will be the time to complete a 100 meter timed test (100M)²⁰.

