13. STATISTICAL CONSIDERATIONS

Age-corrected 100M will be considered as the primary outcome, and will be evaluated using a two-one-sided t-test to test equivalency between treatment arms in the change from baseline to 6 months. In addition, repeated measures ANOVA will be used to determine whether the trajectory across all three time points (baseline, 3mo, 6mo) differs by treatment group. Strength testing/dynamometry, NSAA, 4-stair climb, and time to arise from floor scores will be secondary outcomes, and will also be compared by treatment group using repeated measures ANOVA. Biomarkers studies will be considered exploratory outcomes.

Power: Prior studies evaluating the 100m walk test among patients with DMD have shown an average change over 6 months of -2.9 ± 7.8 . An effective sample size of 10 patients per group will provide 80% power to declare equivalency with an equivalence margin of $\pm 10.6^{21}$.

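### Section 5.1 judges equal efficacy partly by dynamometry and the 4-stair climb, but section 13 gives these only a difference test, with no planned estimate or interval that could support a similarity statement

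*Combined protocol and SAP*

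**What the plan says.** Section 5.1 says the trial will answer whether spironolactone is as efficacious as prednisolone, "as judged by the age-corrected 100 meter timed test and by dynamometry scores derived maximum voluntary isometric contraction testing of selected muscles". The sentence goes on to add the 4-stair climb ("contraction testing of selected muscles and the time to climb 4 stairs").

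Section 5.2 states the hypothesis that "spironolactone and prednisolone are of equal efficacy in improving skeletal muscle function over a 6-month period". It adds "One outcome is that both drugs demonstrate equal efficacy in motor function" and says such a result would serve as pilot data for a longer study.

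Section 6.1 opens: "The primary objective of this trial is to determine whether spironolactone has similar efficacy to glucocorticoids in improving muscle strength". It then names 100M as the primary outcome measure. Strength itself is a secondary outcome in the synopsis: "Muscle strength as measured by dynamometry score, a composite score made up of values from maximum voluntary isometric contraction testing".

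The operative text is narrower. The synopsis objective asks about equivalent improvement in 100M alone. Section 13, repeated in the synopsis, gives 100M two one-sided t-tests on the change to 6 months, with a margin of ±10.6. It also gives 100M a repeated measures ANOVA, described as testing whether the trajectory differs by group. The other four measures "will be secondary outcomes, and will also be compared by treatment group using repeated measures ANOVA". For these four, the documents state no margin, between-arm estimate, confidence interval or rule for reading a non-significant result.

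**The concern.** Two of the three measures that section 5.1 names as judges of equal efficacy have no planned analysis that can speak to similarity. A repeated measures ANOVA asks whether the arms differ. If it is non-significant, the arms may be alike or the trial may be too small to tell, and the test does not say which. The plan recognises that similarity needs its own test, because it specifies one for 100M.

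At stake is how the strength and stair-climb results can be used. Section 5.2 looks ahead to a longer study built on an equal-efficacy finding in motor function. For these measures that study would need an estimated difference with its uncertainty, and the plan does not ask for one.

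**Working it through.** **The plan's own figure first.** Inputs from section 13: SD of 6-month 100M change 7.8, margin 10.6, 10 per arm. Assumed: true difference 0 and one-sided 5% for each test. The standard error is 7.8 × √(2/10) = 3.49, and t(0.95, 18 df) = 1.734. With the SD held at 7.8, the estimate must fall within 10.6 − 1.734 × 3.49 = 4.55 of zero, so power = 2Φ(4.55/3.49) − 1 ≈ 81%. Integrating over the sampling distribution of the pooled SD gives 79.8%. The stated 80% reproduces. In SD units the margin is 10.6/7.8 = 1.36.

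**How often the ANOVA misses a real difference in a secondary outcome.** The documents give no SD for the secondaries, so the unit is the SD of 6-month change. Assumed: normality, compound symmetry, two-sided 5%. The group-by-time test has 2 and 2(N − 2) df, where N is the total number of boys. With SD of change equal to 1, the within-boy error variance is 0.5. With n boys per arm the noncentrality is then (n/2) × Σ(δₜ − δ̄)² / 0.5 = n × Σ(δₜ − δ̄)², where δₜ is the between-arm difference at each of the three visits. Within-boy correlation does not enter in these units.

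Three effect shapes were tried for a Month 6 difference d: half present at Month 3, all present by Month 3, none until Month 6. For d = 1 and n = 10:

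- Half at Month 3, (0, 0.5, 1): Σ = 0.5, noncentrality 5.0, critical F(2, 36) = 3.26, power 46.9%.
- All by Month 3, (0, 1, 1), or none until Month 6, (0, 0, 1): Σ = 0.667, noncentrality 6.67, power 59.4%.

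Across the three shapes:

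| True Month 6 difference | Missed, 10 per arm | Missed, 12 per arm |
|---|---|---|
| 0.5 SD | 82-85% | 79-83% |
| 1 SD | 41-53% | 31-45% |
| 1.36 SD | 14-26% | 8-17% |

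80% power needs a difference of 1.25-1.45 SD at 10 per arm and 1.14-1.31 SD at 12.

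**What an interval would show.** For unadjusted change the 90% CI half-width at 10 per arm is about 1.734 × √(2/10) = 0.78 SD. For Month 6 ANCOVA with baseline as covariate, simulation (20,000 replicates, within-boy correlation assumed 0.5 to 0.8) gives a mean half-width of 0.68-0.75 SD at 10 per arm and 0.62-0.67 SD at 12.

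With no true difference, among trials where the ANOVA is non-significant:

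| 90% CI reaches | 10 per arm | 12 per arm |
|---|---|---|
| 1 SD | 43-56% | 29-41% |
| 1.36 SD | 9-16% | 4-8% |

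The documents set neither threshold for these outcomes. The second only carries the 100M margin across.

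**The case against.** The strongest reply is that nothing operative is wrong. These are secondary outcomes in a 24-boy pilot. 100M is the sole primary outcome, and the synopsis objective is equivalence on 100M alone. The broader wording sits mostly in background and rationale, and section 6.1 goes on to name 100M. All of this is correct. It limits the point to a mismatch between the stated question and the planned secondary analysis, but it does not remove the mismatch.

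A reader might infer that the sponsor intends to read a non-significant ANOVA as equal efficacy. The documents do not say so. They only leave open how such a result will be read.

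A reader might also infer that a non-significant ANOVA is worthless at this size. That goes too far. At 1.36 SD its power is 74-86% at 10 per arm and 83-92% at 12, so it carries some information about differences that large. The 1-SD interval results look much worse than those at 1.36 SD, and the documents favour neither benchmark, so both are shown.

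Finally, a Month 6 contrast with an interval could be taken from the planned repeated measures model, so ANCOVA is not strictly required. That is fair. What is required is that one estimate and one model be named in advance. ANCOVA is a simple choice, and its interval is somewhat narrower than that for unadjusted change.

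**Conclusion.** The point holds for the secondary outcomes. The planned ANOVA cannot support a similarity statement on dynamometry or the 4-stair climb, although section 5.1 makes both of them judges of equal efficacy. The same gap affects NSAA and time to arise, which 5.1 does not name. Confidence in the mismatch is high. Its size is conditional on normality, compound symmetry, a two-sided 5% level, an assumed correlation range for the interval results, and SD units in place of SDs that the documents do not give. Normality is open to question for the timed measures.

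It would be wrong to conclude that the primary result is compromised: the 100M equivalence test, its margin and the sample size are untouched. It would also be wrong to conclude that the secondaries need equivalence margins, because the documents give neither an SD nor a clinical basis for one. This is a change that should be made, but it does not threaten the trial's main analysis.

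**What to change.** 1. For each secondary outcome, make the Month 6 between-arm difference with its 90% CI the main secondary result. Take it from one prespecified model: ANCOVA with the baseline value as covariate. Keep the repeated measures ANOVA as supportive, and leave the 100M analyses as written.
2. Add to section 13 and the matching synopsis text: *Equivalence will be claimed for 100M only. A non-significant difference in a secondary outcome will not be read as equal efficacy.*
3. Align sections 5.1, 5.2 and 6.1 so that 100M alone judges equivalence and the strength and stair-climb results are described as supportive estimates.
4. Do not add margins for the secondaries.

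The cost is some wording and one extra estimate per secondary outcome, with no new visits, data or boys. There are downsides. The intervals will be wide, about ±0.7 SD at 10 per arm. There will be no equal-efficacy verdict on strength or stair climb. The secondaries will be baseline-adjusted while the primary test stays on change from baseline. Power is not the reason to do this: for 1 SD at 10 per arm, ANCOVA has 58-66% against 47-59% for the ANOVA. The gain is nil at correlation 0.8 when the effect is all present by Month 3 or absent until Month 6.

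### Cheap improvement: the four secondary outcomes rest on repeated measures ANOVA alone, which yields no Month 6 treatment difference and, in its classical form, uses only boys with all three visits

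*Combined protocol and SAP*

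**What the plan says.** Section 13 (Statistical Considerations), repeated in the synopsis, sets out two kinds of analysis.

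- **Primary, 100M.** Age-corrected 100M is assessed with a "two-one-sided t-test to test equivalency between treatment arms in the change from baseline to 6 months".
- **100M trajectory.** In addition, "repeated measures ANOVA will be used to determine whether the trajectory across all three time points (baseline, 3mo, 6mo) differs by treatment group".
- **Secondary outcomes.** Dynamometry, NSAA, 4-stair climb and rise time "will also be compared by treatment group using repeated measures ANOVA". This is their only analysis.

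Neither place says which ANOVA term is tested for the secondary outcomes, which boys are analysed, what covariance structure is assumed or how missing visits are handled. No Month 6 contrast is named for them.

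Other sections bear on this. Section 7.2 plans for 10% drop-out. Section 8.5 lists missed appointments among the reasons for withdrawal. Table 3 places strength and functional tests at screening, Month 3 and Month 6 only.

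**The concern.** There are two weaknesses.

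1. **Incomplete boys.** Classical repeated measures ANOVA is fitted to subjects with a value at every time point. A boy aged 4 to 7 who misses one test, or who leaves after Month 3, then contributes nothing to that outcome. The plan expects some loss and does not call for a method that keeps partial records.

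2. **What is estimated.** With baseline as one of three levels, the group-by-time term is a 2-df test of whether the profiles differ in shape. It gives a p-value but no Month 6 difference. For 100M the equivalence test fills that gap; for the four secondary outcomes nothing does. The hypothesis in Section 5.2 is equal efficacy, so a reader will want the size of the Month 6 difference and its uncertainty. A non-significant test of difference in 24 boys would not show similarity.

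**Working it through.** **Inputs from the plan.** Enrolment: "A total of 24 subjects are expected to be enrolled in this trial, with 12 randomized to each treatment group". Change in 100M: "an average change over 6 months of -2.9 ±7.8". Power basis: "An effective sample size of 10 patients per group", giving "80% power to declare equivalency with an equivalence margin of ±10.6". Drop-out is 10% (Section 7.2).

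**Assumed, because the plan gives no figure.** Alpha is 0.05 per one-sided equivalence test and two-sided 0.05 for ANOVA. The rate of missing Month 3 alone is 0 to 10%. Visit noise SD is 2.5 to 5 and between-boy SD is 15. The true Month 6 difference is 10.6, which borrows the 100M equivalence margin as an effect size. Missingness is completely at random.

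**Step 1. The plan's own figure.** SE = 7.8 × √(2/10) = 3.49. Exact power of the two one-sided t-tests, with 10 per arm, margin 10.6 and true difference 0, is 79.8%, so the stated 80% reproduces. Also 10/0.90 = 11.1, rounded up to 12 per arm and 24 in total, which matches. No power is stated for any repeated measures ANOVA, so no stated figure is contradicted.

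**Step 2. Boys with all three visits.**
- Drop-out only: 24 × 0.90 = 21.6.
- Drop-out plus 10% of the rest missing only Month 3: 24 × 0.90 × 0.90 = 19.4. Boys with a Month 6 value remain at 21.6.

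**Step 3. What deletion alone costs.** The variance of the Month 6 contrast was compared using all available visits and complete cases only (generalised least squares, known variance). Baseline-to-Month 6 correlations were 0.5, 0.7 and 0.85, with equal or decaying correlation between visits.
- Drop-out only: complete cases keep 95–99% of the information. Example (0.7, equal): (3.068/3.095)² = 0.983.
- With 10% missing Month 3 only: 86–89%. Example: (3.069/3.262)² = 0.885.

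**Step 4. Power, group-by-time ANOVA against Month 6 ANCOVA.** Simulation with 12 per arm, random slopes plus visit noise, SD of 6-month change 7.8, effect 10.6 at Month 6. ANOVA uses complete cases with Greenhouse–Geisser correction. ANCOVA uses every boy with a Month 6 value.

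| Effect shape | Missing | ANOVA | ANCOVA |
|---|---|---|---|
| Linear to Month 6 | 10% at each follow-up | 72–80% | 83–85% |
| Full by Month 3, or absent until Month 6 | 10% at each follow-up | 86–93% | 82–84% |

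For a linear effect with only 10% lost at Month 6, the gap runs from 2 points in favour of ANOVA to 6 against.

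**Step 5. A smaller effect.** True difference 7.8, correlation 0.7, 10% drop-out, equal or decaying correlation between visits.
- Half the effect at Month 3: ANOVA 48–57% against ANCOVA 64–65%. With 10% Month 3 misses added, 43–52% against 63–64%.
- Full effect at Month 3: 61–74% against 64–65%. With misses, 55–65% against 63%.

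The direction therefore depends on effect shape and on the correlation between visits.

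**Step 6. If the group main effect were the test.** It averages over baseline, where no effect can exist. A linear effect gives (0 + ½ + 1)/3 = ½ of the Month 6 difference, or 5.3. With between-boy SD 15, SE ≈ 15 × √(2/12) = 6.12 and 5.3/6.12 = 0.87, so power ≈ Φ(0.87 − 1.96) + Φ(−0.87 − 1.96) ≈ 14%. Simulated power across the three effect shapes was about 8–20%.

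**The case against.** The strongest reply is that these are unpowered secondary analyses in a 24-boy pilot, and that the numbers do not show repeated measures ANOVA to be generally inferior. Much of that stands. Four stronger readings are tempting and should not be drawn.

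- **That the plan discards every boy with a missed test.** Complete-case analysis is the default of the classical procedure. The documents state no deletion rule.
- **That all secondary outcomes and the 100M trajectory lose power.** Steps 4 and 5 show the result reversing with the effect shape and the correlation. At the planned drop-out alone, deletion costs 1–5% of the information.
- **That the secondary outcomes are tested by the group main effect.** The wording allows it, but Section 13 has just introduced the ANOVA as a test of trajectory, so group-by-time is the more natural reading. The 8–20% figure applies only to the less natural one.
- **That the 100M Month 6 question goes unanswered.** The equivalence test addresses it directly, and a multi-df test is a reasonable answer to a trajectory question.

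The sphericity assumption is a minor matter: in simulation the uncorrected false-positive rate was 4.8–6.8%, and a standard correction exists.

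Two limits on the working also stand. SD 7.8 and 10.6 belong to 100M, and their transfer to the secondary outcomes is an assumption. The comparator in Steps 4 and 5 was a Month 6 ANCOVA; the exact mixed model proposed below was not fitted.

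The objection does not supply the missing estimate. Four outcomes still have no defined Month 6 difference and no stated way of using partial records.

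**Conclusion.** The point holds as an inexpensive improvement, not as an error that undermines the trial. The firm part needs no simulation: the only analysis named for four outcomes gives no Month 6 difference or interval, takes baseline as an outcome level and, in its classical form, uses only complete boys (about 21.6 of 24 at the planned drop-out; 19.4 if another 10% miss only Month 3).

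The power consequence is conditional. It is a loss of roughly 3 to 12 points for a linear effect with 10% missing at each follow-up, and can be no loss or a gain for other shapes. It rests on the borrowed SD of 7.8, an assumed effect of 10.6, assumed visit noise and an assumed rate of Month 3 misses. The primary 100M equivalence test and its stated power are unaffected.

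**What to change.** In Section 13 and the synopsis:

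1. Replace repeated measures ANOVA with a mixed model for the Month 3 and Month 6 values. Fixed effects are treatment, visit, treatment-by-visit and the outcome's own baseline. Use unstructured covariance and REML with Kenward–Roger degrees of freedom. Include every boy with a baseline and at least one follow-up value.
2. For each secondary outcome, report the Month 6 treatment difference with its confidence interval. The interval matters because the model's p-value is still a test of difference and cannot by itself support similarity.
3. For the 100M trajectory, use the joint 2-df test of treatment and treatment-by-visit from the same model. Treatment-by-visit alone would miss a difference that is already complete at Month 3 and stays constant.
4. Keep the two one-sided tests as the primary analysis.

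**Cost.** A few sentences in two places, with no new data or visits. The model relies on data being missing at random, a weaker assumption than complete-case ANOVA needs. A single Month 6 contrast can be less powerful than the 2-df test for some effect shapes, as Step 4 shows; in return it gives an estimate that can be interpreted.
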